8.2.2 Physical Examinations Data

Physical examinations are scheduled at the Month 6, 12, 18, and 24 visits of the open-label treatment period, following the baseline/screening visit. Physical examination findings will be listed by subject and visit.

8.2.3 Body Weight, Waist Circumference, and Height Data

8.2.3.1 Data Collected in the Open-label Treatment Period

During the 24-month open-label treatment period, body weight and waist circumference will be assessed at the following scheduled visits: Weeks 1, 2, and 4 and Months 2, 3, 4, 6, 8, 10, 12, 15, 18, 21, and 24; whereas height will be assessed at the scheduled visits Months 6, 12, 18, and 24 only. For a postbaseline visit where both body weight and height are assessed, BMI (unit: kg/m²) will be derived by dividing weight in kilograms by square of height in meters. For the postbaseline visits where body weight and height are not assessed on the same day, BMI will not be derived, and the values will be set to missing. Specifically for de novo subjects, if weight and height are both taken at Day 1 (predose), then weight and height from Day 1 will be used to calculate the baseline BMI. Otherwise, the most recent weight and height (taken on the same day) prior to Day 1 will be used to calculate the baseline BMI.

For the 24-month open-label period, change from baseline in each of the above 4 parameters will be summarized on OC data by visit and additionally on the LOCF data for the last assessment visit. The number and percentage of subjects having had

significant weight gain (defined as $\geq 7\%$ increase in body weight relative to baseline) and significant weight loss (defined as $\geq 7\%$ decrease in body weight relative to baseline) during the open-label treatment period will be respectively tabulated by visit as well as for the overall open-label treatment period.

Weight z-score is a variable of interest to be derived due to the natural growth of children and adolescent subjects. It describes how similar a subject is to his or her age and gender peers by determining a multiple of the SD from the expected weight. For each scheduled visit, weight z-score is calculated as the deviation of the subject's weight from the mean weight of the reference population divided by the SD for the reference population.

Weight z-score and change from baseline in weight z-scores will be summarized by visit on the OC data by using descriptive statistics for continuous variables. Height z-score and BMI z-score will be similarly calculated and similarly summarized as that for weight, based on the OC data.

Furthermore, the number and percentage of subjects with a large magnitude of change such as ≥ 0.5 or ≤ -0.5 in BMI z-score (relative to baseline) will be tabulated by visit as well as for the overall 24-month open-label treatment period. Refer to [Section 8.2.3.3](#) for the calculations of z-score for body weight, height, and BMI.

If a subject has repeat measures in a lab test for the same visit, the last repeat for the visit will be used for the analysis or summary. However, all data from the same visit, including repeats and unscheduled visits, will be included for the data listing.

8.2.3.2 Data Collected in the Conversion Period

Body weight and waist circumference will be assessed weekly on the subset of de novo subjects that underwent a 1- to 4-week cross-titration conversion period. The analysis and reporting of the data for the conversion period will be analogous to that for the open-label treatment period, with the exception that z-scores will not be calculated or reported for the conversion period.

8.2.3.3 Calculations of z-scores for Body Weight, Height, and BMI

Age and gender adjusted z-scores for body weight, height, and BMI will be calculated using the approach of the Center for Disease Control and Prevention (CDC), US.

The CDC provides a reference dataset (CDCref_d.sas7bdat in sas data format or CDCref_d.csv in csv data format) and a sas program (cdc-source-code.sas) along with detailed instructions for the calculations at <https://www.cdc.gov/growth-chart-training/hcp/computer-programs/sas.html>.

The Z-scores are calculated as $Z = [((\text{value} / M)^{\text{**L}}) - 1] / (S * L)$, in which 'value' is the child's BMI, weight, height, etc. The L, M, and S values are in the reference dataset and vary according to the child's sex and age. The following rules will be observed:

- 1) Age (in months) at the day of assessment, which is an input for the calculations, will be calculated as: (assessment date – birth date + 1)/(365.25/12).
- 2) In principle, BMI and its z-score will be calculated only if weight and height are both taken on the same day.
- 3) The above calculations are applicable in children and adolescents older than 24 months but younger than 20 years of age.

It is not anticipated that the CDC's information (including the reference dataset, the SAS program, or the instructions for the calculations) will be updated in the short run.

Nevertheless, the information at the CDC website will be re-checked for any updates within a month prior to the database lock, and updated information will be used if any.

8.2.4 Vital Signs Data

8.2.4.1 Data Collected in the Open-label Treatment Period

Vital signs will be assessed at all scheduled visits across the 24-month open-label treatment period. Vital signs parameters include body temperature, systolic blood pressure (SBP), diastolic blood pressure (DBP), and pulse (ie, heart rate), of which SBP and DBP and pulse will be measured in the supine, sitting, and standing positions.

Measurements obtained in different positions will be treated as different parameters for purposes of the data summary. Thus, there are a total of 10 vital signs parameters for this trial.

For the 24-month open-label treatment period, assessment values and change from baseline values in each vital signs parameter will be summarized on the OC data by visit and additionally on the LOCF data for the last assessment visit.

Additionally, change from baseline to the lowest value postbaseline and to the highest value postbaseline in each parameter will be respectively summarized on the OC data for the overall 24-month open-label treatment period.

Potentially clinically significant vital signs abnormalities during the 24-month open-label treatment period will be identified, and the incident (ie, number and percentage of subjects who had such an abnormality) in each parameter will be tabulated by visit and at the subject level for the overall open-label treatment period. All potentially clinically significant vital signs abnormalities will be listed by prior treatment group, subject ID, visit, and vital signs parameter, along with baseline value, age, sex, body weight, and

dose at onset of the event of abnormality. Refer to Appendix 1 of the protocol for the criteria for identifying vital signs of potential clinical relevance. In addition to the protocol criteria, blood pressure criteria provided in Appendix 2 will be applied.

If a subject has repeat measures in a parameter at a visit, only the last repeat for the visit will be used for the analysis or summary. But all data from the same visit, including repeats and unscheduled visits, will be used for the data listing.

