**Appendix 1****Criteria for Identifying Vital Signs of Potential Clinical Relevance**

| Variable                              | Criterion Value a  | Change Relative to Baseline a           |
|---------------------------------------|---|--|
| Heart Rate b               | > 120 bpm
< 50 bpm   | ≥ 15 bpm increase
≥ 15 bpm decrease             |
| Systolic Blood Pressure b  | > 180 mmHg
< 90 mmHg   | ≥ 20 mmHg increase
≥ 20 mmHg decrease           |
| Diastolic Blood Pressure b | > 105 mmHg
< 50 mmHg   | ≥ 15 mmHg increase
≥ 15 mmHg decrease           |
| Orthostatic Hypotension               | ≥ 20 mmHg decrease in systolic blood pressure and a ≥ 25 bpm increase in heart rate from supine to sitting/standing | Not Applicable
(baseline status not considered) |
| Weight                                | -   | ≥ 7% increase
≥ 7% decrease                     |

aIn order to be identified as potentially clinically relevant, an on-treatment value must meet the “Criterion Value” and also represent a change from the subject’s baseline value of at least the magnitude shown in the “Change Relative to Baseline” column.

bAs defined in “Supplementary Suggestions for Preparing an Integrated Summary of Safety Information in an Original NDA Submission and for Organizing Information in Periodic Safety Updates,” FDA Division of Neuropharmacological Drug Products draft (2/27/87).

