10.2 Visit Window and the Derived Analysis Visit

The variable analysis visit will be derived to facilitate a by-visit analysis (including summary) and reporting. For efficacy parameters (eg, PANSS and CGI-S) and the 3 EPS parameters (ie, SAS, AIMS, and BARS), the analysis visit will be derived per Table 10.2-1 below. For all other parameters, the protocol-specified scheduled visit as recorded on the eSource *per se* will be simply taken as the analysis visit, and observations or assessments collected at any unscheduled visits will be programmatically mapped to an analysis visit per Table 10.2-1 below.

Protocol Amendment 5 (04 Aug 2021) updated the definition of a month duration for the purpose of scheduling monthly trial visits. The protocol month duration was changed from 4 weeks to 31 days (± 3 days). However, for analysis purposes, the same windowing will apply to all subjects, regardless of whether the assessment occurred before or after the amendment.

- 1) Observations will be mapped to an analysis visit for the 24-month open-label period based on the visit windows shown in Table 10.2-1.

Table 10.2-1 Visit Window for the 24-month Open-label Treatment Period

Analysis Visit	Trial Day	
	Allowed in Protocol	Window Specified in SAP
Day 1	1	1
Week 1	7 \pm 3	2 to 10
Week 2	14 \pm 3	11 to 20
Week 4	28 \pm 3	21 to 44
Month 2	62 \pm 3	45 to 76
Month 3	93 \pm 3	77 to 104
Month 4	124 \pm 3	105 to 160
Month 6	186 \pm 3	161 to 216
Month 8	248 \pm 3	217 to 272
Month 10	310 \pm 3	273 to 328
Month 12	372 \pm 3	329 to 412
Month 15	465 \pm 3	413 to 496
Month 18	558 \pm 3	497 to 580
Month 21	651 \pm 3	581 to 664
Month 24	744 \pm 3	665 to 790

Note: If the observation occurs 7 days after the last dose date, then Table 10.2-1 should not be used.

- 2) A subset of de novo subjects will undergo a 1- to 4-week conversion period to cross-titrate to brexpiprazole monotherapy from other antipsychotic medications. Observations in the conversion period will be mapped to an analysis visit of the conversion period based on the first dose date for the conversion period as shown in Table 10.2-2.

Table 10.2-2 Visit Window for the Conversion Period		
Analysis Visit	Allowed in Protocol	Specified in SAP
Day 1 (Conversion Period)	Day 1 in the conversion period	Same as that in protocol
Week 1 (Conversion Period)	Day 4 to 10 in the conversion period	Day 2 to 10 in the conversion period
Week 2 (Conversion Period)	Day 11 to 17 in the conversion period	Same as that in protocol

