Week 3 (Conversion Period)	Day 18 to 24 in the conversion period	Same as that in protocol
Week 4 (Conversion Period)	Day 25 to 31 in the conversion period	Same as that in protocol

Note: Day # in the conversion period = observation date in the conversion period – date of the first dose of IMP in the conversion period + 1.

The above algorithm ensures that all observations that are obtained at unscheduled visits will be mapped to an analysis visit. In case that multiple observations of the same parameter on the same subject are mapped to the same analysis visit, only the last observation (in the visit window) will be used for the by-visit analyses, but all observations will be included for the data listing.

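### The SAP's last-value rules make no exception for abnormality incidence, so a normal repeat can displace a qualifying value in some secondary safety tables

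*SAP*

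**What the plan says.** **Vital signs (SAP 8.2.4.1).** The number and percentage of subjects with an abnormality "will be tabulated by visit and at the subject level for the overall open-label treatment period". Later in the section, for a subject with "repeat measures in a parameter at a visit, only the last repeat for the visit will be used for the analysis or summary"; all repeats and unscheduled values go to the listing. The section also states "All potentially clinically significant vital signs abnormalities will be listed".

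**Visit windows (SAP 10.2).** For parameters other than efficacy and EPS scales, the recorded scheduled visit is the analysis visit, and "observations or assessments collected at any unscheduled visits will be programmatically mapped to an analysis visit" using Table 10.2-1. Where several values fall on one analysis visit, "only the last observation (in the visit window) will be used for the by-visit analyses".

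**Laboratory tests.** SAP 8.2.1 has no repeat rule. One sits in 8.2.3.1, the weight and height section, for a subject with "repeat measures in a lab test for the same visit, the last repeat for the visit will be used for the analysis or summary".

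**Criteria.** SAP 8.2.1, 8.2.4.1 and 8.2.5 adopt protocol Appendices 2, 1 and 3 respectively. The footnote in protocol Appendix 1 begins "In order to be identified as potentially clinically relevant, an on-treatment value must meet the" tabulated criterion, and adds a minimum change from baseline. Appendix 3 has the same footnote. Neither asks for confirmation by a repeat.

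**The one any-value rule.** The treatment-emergent glucose and lipid analysis (SAP 8.2.1 and SAP Appendix 1) counts a single qualifying observation at any time after baseline.

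**The concern.** Incidence of clinically significant abnormalities is a named secondary safety endpoint (protocol 3.5.2.1). A last-value rule suits a mean by visit, where each subject should contribute one value. An abnormality count asks a different question: did a qualifying value occur?

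Retests are also not random. Protocol 3.7.3.4 asks for one repeat of an ECG judged clinically significant. Protocol 3.7.3.2 calls for unscheduled follow-up of clinically significant laboratory abnormalities, and 5.1 lets the investigator repeat a laboratory test to verify it. Later values therefore tend to follow the very values that the tables are meant to count. At stake are secondary counts that err in one direction and may differ from the listing of the same abnormalities.

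**Working it through.** The plan states no figure to reproduce. The check sets each incidence table against the rule that selects its values, then works out how long a retest can displace a scheduled value.

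**1. Reach of each rule**

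| Count | By visit | Whole period |
|---|---|---|
| Vital signs | Last repeat (8.2.4.1) and last in window (10.2) | Last same-visit repeat (8.2.4.1), not limited to means |
| ECG | Last in window (10.2) | No displacing rule |
| Potential serious hepatotoxicity | Last in window (10.2) | Each subject counted once; reads as ever-occurred, silent on repeats |
| Other laboratory criteria, prolactin multiples of ULN | 8.2.1 does not say whether by visit or overall | Repeat sentence in 8.2.3.1; reach ambiguous |
| Treatment-emergent glucose and lipids (SAP Appendix 1) | – | Any qualifying value |
| Glucose and lipids under protocol Appendix 2 | As other laboratory criteria | As other laboratory criteria; no any-value rule |

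**2. Direction.** Every subject counted under a last-value rule is also counted under an any-value rule, because the last value is one of the values. The last-value count is therefore equal or lower.

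**3. Worked case (hypothetical readings).** SAP Appendix 2 flags systolic pressure above 120 mmHg with a change of at least 15 mmHg. Take a baseline of 108, a visit reading of 126 and a same-visit repeat of 116.
- First reading: 126 > 120 and 126 − 108 = 18 ≥ 15, so it qualifies.
- Repeat: 116 is not above 120 and 116 − 108 = 8 < 15, so it does not.

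The table uses 116 and does not count the subject on this visit. The listing shows the 126.

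**4. Span for by-visit laboratory and ECG rows.** Inputs are the targets and windows in Table 10.2-1. Width = upper − lower + 1; span after an on-target visit = upper − target.

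| Visit | Width (days) | Span (days) |
|---|---|---|
| Week 4 | 44 − 21 + 1 = 24 | 44 − 28 = 16 |
| Month 6 | 216 − 161 + 1 = 56 | 216 − 186 = 30 |
| Month 12 | 412 − 329 + 1 = 84 | 412 − 372 = 40 |
| Month 18 | 580 − 497 + 1 = 84 | 580 − 558 = 22 |
| Month 24 | 790 − 665 + 1 = 126 | limited by the note on values 7 days after last dose |

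Each span shifts by up to 3 days with the visit window. Amendment 5 also matters: "The protocol month duration was changed from 4 weeks to 31 days", while one set of windows serves all subjects. Assuming 28-day months, earlier visits fall on Days 168, 336 and 504, and the spans at Months 6, 12 and 18 become 216 − 168 = 48, 412 − 336 = 76 and 580 − 504 = 76 days.

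These spans show when displacement is possible. They do not show how often it happens, and they bear only on by-visit rows.

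**The case against.** The strongest reply is about reach. For whole-period incidence, no parameter combines an explicit displacing rule with a prescribed retest. Vital signs have the rule, but the protocol prescribes no post-baseline retest, and the rule covers only repeats at the same visit. ECGs have the prescribed retest, but SAP 10.2 is confined to by-visit analyses. For laboratory tests the repeat sentence is misplaced, and the prompts to retest are weaker: one is permissive, and the other follows the screening rule. A subject lost from one by-visit row may still be counted overall. All of this stands, and it limits the point.

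It can also be said that one value per visit is a consistent convention, and that a repeat is a reasonable guard against a spurious reading. That is fair. But if confirmation is intended, the SAP should say so, since the criteria it adopts do not require it.

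A reader might infer that the SAP contradicts the protocol. The documents do not support that: the appendix footnotes say what makes a value qualify, not which values enter a table. A reader might also infer that safety cases are lost. They are not. Listings keep the values, potential serious hepatotoxicity has its own listing and is immediately reportable, medically relevant laboratory values become AEs, and SAP 8.1 adds AE summaries for topics such as QT prolongation, prolactin and hepatic impairment. Vital signs also have summaries of change to the lowest and highest post-baseline value.

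**Conclusion.** The point holds within limits. Displacement is explicit for vital-sign incidence, by visit and overall, when a same-visit repeat is taken. It is also explicit for by-visit incidence of vital-sign and ECG abnormalities and of potential serious hepatotoxicity. For laboratory incidence the text is ambiguous. Overall ECG incidence has no displacing rule, and overall hepatotoxicity reads as ever-occurred.

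Two stronger readings should be resisted. One is that all overall abnormality counts are too low; the rules do not reach that far. The other is that the shortfall can be expressed as a percentage. The documents give no retest rate and no rate at which abnormal values persist, so any such figure would rest wholly on assumption. It would also be wrong to treat glucose and lipids as fully covered: the any-value rule applies only to the SAP Appendix 1 analysis, not to the protocol Appendix 2 criteria.

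What can be said is that the affected counts are equal to or lower than any-value counts and may not match the listings. The primary endpoint is unaffected. Severity is minor and confidence medium, because part of the point rests on how unclear text would be programmed.

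**What to change.** In SAP 8.2.1, 8.2.3.1, 8.2.4.1, 8.2.5 and 10.2, state three rules:

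- **Overall-period incidence:** a subject counts if any post-baseline on-treatment value qualifies, including repeats and unscheduled values. This covers the criteria in protocol Appendices 1 to 3, the blood pressure criteria in SAP Appendix 2, prolactin multiples of ULN, potential serious hepatotoxicity, weight change of at least 7% and the BMI z-score change categories.
- **By-visit incidence:** any qualifying value mapped to that visit counts.
- **By-visit descriptive statistics of continuous values:** the last-value rule stays.

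Move the laboratory repeat sentence from 8.2.3.1 to 8.2.1.

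The cost is SAP wording and one programming flag, with no new data. The downside is that some transient or spurious values will be counted, and a value some weeks from the scheduled assessment can flag that visit. The listings will show these cases.

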8.2.4.2 Data Collected in the Conversion Period

Vital signs data will be assessed weekly on the subset of de novo subjects that underwent a 1- to 4-week cross-titration conversion period. The analysis and reporting of the vital signs data for the conversion period will be analogous to that for the open-label treatment period.

8.2.5 Electrocardiogram Data

A data summary will be provided for the 24-month open-label treatment period only, since there are no ECG measurements in the conversion period.

The ECG measurements will be made at the Week 4 and Month 6, 12, 18, and 24 visits for all enrolled subjects during the 24-month open-label treatment period. The ECG measurements will also be obtained on Day 1 upon entering the open-label treatment period for de novo subjects.

Assessment values and change-from-baseline values in each of the quantitative ECG parameters will be summarized on the OC data by visit and LOCF data for the last assessment visit.

The incidence of clinically significant changes in each ECG parameter will be summarized on the OC data by visit, as well as for the overall open-label treatment period. Refer to Appendix 3 of the protocol for the criteria for identifying ECG measurements of potential clinical relevance. Data of clinically significant changes in ECG parameters will be listed by prior treatment group, subject number, sex, age, body weight, baseline value, visit, description of the findings, and dose at onset of the event.

For the analysis of QT and QTc, data from 3 consecutive complexes (representing 3 consecutive heart beats) will be measured to determine average values. The following QT corrections will be used for reporting purposes in the clinical study report:

- 1) QTcF is the length of the QT interval corrected for heart rate by the Fridericia formula: $QTcF=QT/(RR)^{0.33}$;
- 2) QTcN is the length of the QT interval corrected for heart rate by the Food and Drug Administration (FDA) Neuropharm Division formula: $QTcN=QT/(RR)^{0.37}$.

8.2.6 Other Safety Data

8.2.6.1 Special Pediatric Safety Assessments

A data summary will be provided for the 24-month open-label treatment period only, since in the conversion period there are no special pediatric safety assessments such as the NY-AACENT and UKU Side Effects Rating Scale assessment.

The NY-AACENT will be performed at the baseline visit, all protocol-specified scheduled visits, and at the early termination (ET) visit. The incidence of sign/symptom items as recorded in the NY-AACENT scale will be summarized. Specifically, the incidence (and severity) of the sign/symptom items will be tabulated by trial visit, based on the OC data. The summarization will be repeated for the subset of *drug-related* signs or symptoms and for the subset of *function-impaired* signs or symptoms, respectively. Additionally, change from baseline in the NY-AACENT total score will be summarized on the OC data by trial visit and on the LOCF data for the last assessment visit.

See [Section 8.2.7](#) for the construction of the NY-AACENT total score.

The UKU Side Effects Rating Scale assessments will be administered at the baseline visit, all protocol-specified scheduled visits, and at the ET visit. The incidence (and severity) of the individual side effects and categories of side effects as recorded in the UKU Side Effects Rating Scale will be tabulated by trial visit, based on the OC data. The summarization will be repeated respectively for the subset of having “improbable”, “possible”, and “probably” connection to the IMP. In addition, a by-visit summarization will be provided for the following assessments: (i) the global assessment of the interference by existing side effects with the subject’s daily performance, and (ii) the consequence (ie, the measures taken with respect to the side effects).

